6.5 Assumption Checks and Alternative Analyses

Assumption checks will be performed for the primary and all secondary outcomes according to the statistical methods used to analyzed them.

Weibull and Cox Proportional Hazard Models

The Weibull and Cox proportional hazard regression models assumes that the hazard ratio is constant over time. This will be checked by plotting -log(log(survival)) curves for each treatment against log(analysis time) and assessing if the curves are parallel. If the proportional hazard assumption is deemed to be violated, alternative parametric survival models will be fitted instead. The following survival distributions will be considered: exponential, Gompertz, and lognormal. The goodness-of-fit of each model will be assessed with plots of Cox—Snell residuals against the estimated cumulative hazard function of the residuals, and the one with the best fit will be the chosen model.

Linear Mixed Models

For linear mixed models, we will compare observed and model-predicted outcomes. If we detect a poor-fitting model, we will refit the model with a log-transformation of the outcomes. We do not expect other model-fit problems, due to the simplicity of the model (only a random intercept and a few fixed effects); however, in the unlikely event that we will encounter numerical problems with fitting the model, we will remove the two time point variables and substitute it with a single (linear) variable for time.

Two-sample T test

The discrete numerical outcomes (number of new infections per patient and number of readmissions per patient) are limited to only a few possible values (with no great maximum), and as

such, there is no concern about the distribution of the outcomes, except for the situation where almost all patients have the same number and there is not enough variation in the data to get a meaningful result from the statistical methods. In that case, the outcome will be presented with the table of observed number and percentages in each treatment group in each category only.

7 Safety Analyses

General safety evaluations will be based on the incidence, intensity, and type of AEs, and clinically significant changes in the patient's physical examination findings, vital signs, clinical laboratory results and serum drug concentrations. Safety variables will be tabulated and presented for all patients in the safety set.

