2.3 Sample size

Assuming the time of hospitalization after randomization follows a Weibull distribution with a scale parameter λ = 18 and shape parameter κ =2.2 (corresponding to a median of 15 and an IQR of 10 – 21), we need to include 58 patients: 18 in the placebo group, 10 in the 250 mg/day group, 10 in the 500 mg/day group, and 20 in the 1 g/day group) in order to reach approximately 80% power to show a significant dose-response in this study with a maximal reduction in time of hospitalization of 33%. This calculation is based on optimal designs in dose-finding studies according to the MCPMod methodology with three alternative dose-response curves: linear, e-max and exponential (Pinheiro et al., 2014).

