2.4 Statistical Framework

The statistical framework will be based on the context of dose-finding, for which there are two main approaches: "regression" and "contrast" (Senn, 2007). In the regression approach, the actual doses used in the trial are viewed as samples from a dose continuum, and the purpose is to estimate the dose response curve. In the contrast approach, interest is on one or (more likely) several contrasts between the doses used in the trial. The former is the most explorative and may be sensitive to modeling choices, small number of doses, and over-fitting, especially for small sample sizes (such as in this trial). The latter is well suited for determining the *minimum effective dose*, in which we compare the different doses to placebo.

Specification of the Primary Objective

The primary objective of this study will be to establish the minimum effective dose of NR on shortening recovery time after critical illness. The primary outcome is length of hospital stay in days (see Section 5.1 for details).

There is only one identified primary analysis in this trial. All other efficacy analyses will be regarded as supportive or exploratory.

Hypothesis Setup

Let μ_1 , μ_2 , μ_3 , and μ_4 denote the mean lengths of hospital stay for placebo, low dose (250 mg/day), medium dose (500 mg/day), and normal dose (1 g/day), respectively.

The statistical scheme to account for multiple testing is based on the *closed multiple test procedure* of Marcus et al. (1976). Under the monotonicity assumption, we define a set of elementary null hypotheses (the many-one comparison) with a preassigned order of performing the tests (Williams, 1971):

Step 1: Test the null hypothesis H_0 : $\mu_1 = \mu_4$ Step 2: Test the null hypothesis H_0 : $\mu_1 = \mu_3$ Step 3: Test the null hypothesis H_0 : $\mu_1 = \mu_2$

The test in Step 1 is carried out with a nominal significance level of α = 0.05. If the test is rejected, the test in Step 2 can be carried out, also with α = 0.05. If the test in Step 2 is rejected, the test in Step 3 can be carried out (with α = 0.05). The tests in steps 2 and 3 are only performed if the preceding null hypothesis is rejected, which – together with the monotonicity assumption – ensures that the significance level is preserved for the entire procedure (Williams, 1971; Bauer, 1991). All tests will be performed two-sided.

Decision Rule

The testing scheme above can result in four situations:

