2.6 Timing of Final Analysis

The main analysis is planned to after patients have concluded 90 days of treatment and attended the 65 weeks follow-up appointment. All data will be entered, verified and validated before the primary database will be locked, un-blinded and data analysis commenced.

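### SAP 6.5 allows the primary Weibull model to be replaced by visual judgement after unblinding, so the P value behind the minimum-effective-dose rule is not fixed in advance

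*SAP*

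**What the plan says.** - **One primary test.** SAP 2.4: "There is only one identified primary analysis in this trial". SAP 6.1 specifies it as a Weibull survival model with treatment as the only explanatory variable, reported as a hazard ratio with a test of HR = 1.
- **Level.** SAP 2.4: "The test in Step 1 is carried out with a nominal significance level of α = 0.05"; "All tests will be performed two-sided". Steps 2 and 3 use the same level, each only after the preceding rejection, and the section states that the level is thereby preserved for the whole procedure.
- **Replacement.** SAP 6.5 applies its checks to the primary outcome as well as the secondary ones. Transformed survival curves are plotted for each treatment and inspected for parallelism. Then: "If the proportional hazard assumption is deemed to be violated, alternative parametric survival models will be fitted instead". The candidates are exponential, Gompertz and lognormal, compared on Cox-Snell residual plots, and "the one with the best fit will be the chosen model".
- **Timing.** SAP 2.6 has the database "locked, un-blinded and data analysis commenced", in that order. Protocol 10.4 likewise reveals allocation after lock, and closes amendments to the statistical plan at lock.
- **Safeguards.** SAP 6.1 commits to a figure of every patient's stay, Kaplan-Meier curves for each dose and placebo, and sensitivity analyses that include Cox regression.

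**The concern.** Neither decision in SAP 6.5 has a test, a cut-off, a fit statistic or a blinded assessor. Both are made on plots that separate the treatment arms, after the codes are known, in small groups: 18 + 20 = 38 patients in step 1 and 18 + 10 = 28 in steps 2 and 3. No section keeps the Weibull P value as primary once a replacement is chosen, and none requires the same model in all three steps.

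What is at stake is the rule in SAP 2.4. Step 1 decides whether any effect of NR is declared and whether the lower doses are tested at all. The fixed-sequence argument needs each step to be a valid 5% test, and a test whose model is picked from the treatment-labelled data is not assured to be one. The plan already takes comparable decisions blind elsewhere: SAP 3.2 classifies protocol deviations before unblinding.

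**Working it through.** **1. Design figures.** SAP 2.3 assumes stays with "scale parameter λ = 18 and shape parameter κ =2.2" and claims "approximately 80% power to show a significant dose-response in this study with a maximal reduction in time of hospitalization of 33" per cent.

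- Quartiles, 18 × (−ln(1 − p))^(1/2.2): 10.2, 15.2 and 20.9 days. They match the stated median of 15 and IQR of 10 to 21.
- MCPMod contrast test on log time, 18/10/10/20 patients, one-sided 0.025: average power 78.6 to 80.0% over plausible e-max and exponential shapes (assumed, because the SAP gives none). The stated 80% is reproduced.
- A 33% reduction is a time ratio of 0.67, so the hazard ratio for discharge is 0.67^(−2.2) = 2.41. Step 1 by Schoenfeld: √(38 × (18/38) × (20/38)) × ln 2.41 − 1.96 = 3.078 × 0.881 − 1.96 = 0.75, which is 77.4% power. Simulation gives 76.9%.

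**2. Does the model matter?** Simulated step 1 at the design effect (40,000 trials, two-sided Wald P < 0.05) has power of 76.9% with Weibull, 80.7% with Gompertz, 60.1% with lognormal and 6.6% with exponential. The significance verdict differs between Weibull and lognormal in 22% of trials, and between Weibull and the best alternative by AIC in 12%.

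**3. Type I error in step 1.** 18 v 20, no effect, no deaths, 20,000 trials per setting. The SAP gives no numerical trigger, so a likelihood-ratio test of equal Weibull shape in the two arms stands in for the visual check, at P < 0.05 to P < 0.30. The replacement is chosen by AIC. The lognormal column assumes a log-SD of 0.6.

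| Rule | Weibull stays | Lognormal stays |
|---|---|---|
| Weibull kept throughout | 6.1% | 12.6% |
| Switch followed mechanically | 6.6–7.5% | 8.4–10.7% |
| Smaller of two visible P values taken | 10.0% | 14.7% |
| One choice on pooled blinded stays | 6.4% | 6.9% |

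Repeat simulations gave, for Weibull and lognormal stays respectively:
- model fixed: 5.6–6.2% and 12.3–12.8%
- switch: 6.1–7.3% and 8.0–10.8%
- smaller P value: 9.5–9.9% and 14.3–14.7%
- pooled choice: 5.9–6.3% and 6.4–7.2%

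**4. Reading the table.** Under Weibull stays the switch adds 6.6 − 6.1 = 0.5 to 7.5 − 6.1 = 1.4 points. A very loose trigger (P < 0.50, met in 52% of null trials) adds 8.03 − 6.17 = 1.86 points. The first point above 5% is present with the model fixed; it is a small-sample Wald effect and not due to SAP 6.5. In trials where the switch is triggered, the replacement rejects in about 10 to 13%, against about 6% for the Weibull. Under lognormal stays the switch reduces the error.

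**5. Steps 2 and 3.** With 18 v 10 and Weibull stays, size is 6.7% fixed and 7.2%, 7.8% or 8.5% with triggers at P < 0.05, 0.20 or 0.50.

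**The case against.** The strongest reply is that this discretion is bounded and its effect small. The type of check and the three alternatives are written down in advance. SAP 6.1 promises individual stays, Kaplan-Meier curves and a Cox analysis, so a reader can judge parallelism and see a competing P value. All of that stands. What a reader cannot see is the threshold that was applied, and none of these safeguards settles which P value is primary.

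A second reply is that the mechanical figures do not measure subjectivity. The simulated switch never looks at the treatment P value, so its excess comes from data-dependent switching to a list that omits Weibull. That is correct. Only the 10.0% and 14.7% rows represent choosing with results in view.

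A reader might infer from the unblinding order that the analyst will hold the Weibull P value and its replacement side by side and take the smaller. The SAP does not describe this. Curves by arm do show the separation between groups, and nothing prevents the comparison, but those two figures are ceilings and not expected values. Likewise, the SAP is silent on using different models in different steps; it does not plan to.

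Third, a fallback is worth having: under lognormal stays the fixed Weibull test is the worse one. This stands, and it shapes the fix.

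**Conclusion.** The point holds as a modest one that should be corrected. The primary P value can change model after unblinding through two visual judgements without criteria, so the 5% level in SAP 2.4 is not assured. It would go too far to say that SAP 6.5 destroys error control: under the SAP's own Weibull assumption, mechanical use adds about 0.5 to 1.4 points to a size of about 6%, and part of that 6% exists anyway. About 10% is a ceiling for choosing between two visible P values. If stays are lognormal, a fixed Weibull test has about 12 to 13% and the switch lowers this to about 8 to 11%. The fault is therefore the unblinded, criterion-free choice and not the existence of an alternative model.

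These sizes assume no in-hospital deaths, Wald tests, a formal stand-in for the visual trigger and, for the second scenario, a log-SD of 0.6.

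**What to change.** - **SAP 6.5.** State that the survival distribution is chosen once, before treatment codes are released, on the pooled stays of all 58 patients by AIC, with Weibull among the candidates, and is used in all three steps. Write this rule in before database lock.
- **SAP 6.1.** State the effect measure for each candidate: hazard ratio for Weibull, Gompertz or exponential; time ratio, with a test of ratio = 1, for lognormal. This is needed because lognormal has no constant hazard ratio, and in simulation the pooled choice picked it in 8% of null Weibull trials, 14% at the design effect and 92% when stays were lognormal.
- **After unblinding.** Proportional-hazards plots and any other model are sensitivity analyses and cannot replace the primary P value.

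**Cost.** New wording and one blinded model fit. If stays are Weibull, step 1 loses about 2 to 3 points of power (for example 76.8% to 74.4% at a 33% reduction); if lognormal, about 0.4 to 1 point. A pooled choice cannot detect non-proportional hazards between arms. With equal means but unequal shapes (2.2 v 4.0, or 3 v 1.5, both assumed) its size is still 9 to 12%, against 12 to 18% for the present switch, so the plots by arm should still be reported.

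Keeping Weibull as primary whatever the plots show would be simpler and preserve the hazard ratio, but it leaves the 12 to 13% size under lognormal stays.

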6.1 Primary Outcome

The primary outcome is length of hospital stay (time to discharge), measured in number of days, and the primary analysis of the primary outcome will be performed on the full analysis set (FAS). A secondary (sensitivity) analysis of the primary outcome will be performed on the per protocol set (PPS).

Statistical Method for Steps 1-3

The comparison of the length of hospital stay between the NR and placebo groups – in each of the three steps – will be carried out with a Weibull survival model, with time as the number of days of hospital stay and treatment (NR vs placebo) as explanatory variable. The estimated treatment effect will be the hazard ratio (HR) for treatment with a 95% confidence interval.

Presentation of Results

The estimated treatment effect (HR) with a 95% confidence interval will be presented, together with the P-value for the null hypothesis of a zero-treatment difference (HR = 1).

The observed mean and standard deviation for placebo and each dose will be presented in a figure, along with the observed values (length of hospital stay) for each individual, as a scatter with connected lines-plot. Figure 1 shows an example with simulated data.

A plot of the Kaplan-Meier survivor function (for time to discharge) of each dose and placebo will be presented.

[figure not shown]

Figure 1: Simulated data

Missing Data

We will have complete data on the length of hospital stay, except for the following situation: A patient dies before being discharged from the hospital. In this case, the patient will be censored at the time of death. Imputation of the length of hospital stay will be performed as a sensitivity analyses (see item 3 below).

Sensitivity Analyses

The following sensitivity analyses will be performed on the primary outcome:

- 1. As described above but on the per protocol set (PPS)
- 2. As described above but with Cox proportional hazard regression instead of Weibull regression
- As described above but with Cox proportional hazard regression and imputation (instead of censoring) of the length of hospital stay with the maximum length of hospital stay (regardless of treatment group) for patients who die before discharge

Subgroup Analyses

There will be no subgroup analyses.

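### Two of the three models that SAP 6.5 offers when proportional hazards fails assume proportional hazards themselves, and no effect measure is named for the third

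*SAP*

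**What the plan says.** SAP 6.1 analyses length of stay in each of the three ordered steps with a Weibull model that has "treatment (NR vs placebo) as explanatory variable". It defines one effect measure: "The estimated treatment effect will be the hazard ratio (HR) for treatment with a 95% confidence interval". The reported P-value is for HR = 1.

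SAP 6.5 recognises that the Weibull and Cox models need a constant hazard ratio and checks this by eye, from transformed survival curves that should be parallel. It then says: "If the proportional hazard assumption is deemed to be violated, alternative parametric survival models will be fitted instead". The candidates are listed: "The following survival distributions will be considered: exponential, Gompertz, and lognormal". Each is judged on plots of Cox-Snell "residuals against the estimated cumulative hazard function of the residuals", and "the one with the best fit will be the chosen model".

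The SAP does not let a shape parameter depend on treatment, add a treatment-by-time term, or name an effect measure other than the HR for this outcome. The protocol gives no fallback model.

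**The concern.** A remedy for non-proportional hazards should relax proportional hazards. Two of the three candidates do not, and the selection rule does not steer the analyst to the one that does. The trial could report that non-proportionality was found and dealt with, and still present a single hazard ratio that hides it. If lognormal is chosen instead, the SAP has not said which estimate takes the place of the promised HR, so that choice would be made after the data are seen. SAP 2.4 identifies only one primary analysis, and this is its only stated answer to non-proportional hazards. The Cox sensitivity analyses in SAP 6.1 make the same assumption and do not fill the gap.

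**Working it through.** **1. The plan's own distribution.** SAP 2.3 assumes Weibull stays with scale 18 and shape 2.2. The quantile is 18 × (−ln(1−p))^(1/2.2). For p = 0.25, 0.50 and 0.75 this gives 10.2, 15.2 and 20.9, which agrees with the stated median of 15 and IQR of 10 to 21. These figures are not in dispute; the distribution serves as the placebo arm below.

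**2. What each model assumes.** Let x = 1 for NR and 0 for placebo, with x the only covariate (SAP 6.1).

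- Weibull: h(t) = κ t^(κ−1) exp(b0 + b1x), so h1/h0 = exp(b1) at every t.
- Exponential: h(t) = exp(b0 + b1x), so h1/h0 = exp(b1) at every t. This is the Weibull with κ = 1, so its maximised likelihood cannot exceed that of the model it replaces.
- Gompertz: h(t) = exp(b0 + b1x) exp(γt), so h1/h0 = exp(b1) at every t.
- Lognormal: log T = b0 + b1x + σε. The hazard ratio changes with t. What is constant is the time ratio exp(b1).

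This step is algebra and depends on no assumed data.

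**3. An illustration.** Assumed: placebo Weibull(18, 2.2), NR Weibull(12, 1.1), 20,000 per arm so that sampling error is negligible. The true ratio is [1.1/12 × (t/12)^0.1] / [2.2/18 × (t/18)^1.2].

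| Day | 2 | 5 | 10 | 20 | 30 |
|---|---|---|---|---|---|
| True HR | 8.76 | 3.20 | 1.49 | 0.70 | 0.45 |
| Weibull fit | 1.39 | 1.39 | 1.39 | 1.39 | 1.39 |
| Exponential fit | 1.38 | 1.38 | 1.38 | 1.38 | 1.38 |
| Gompertz fit | 1.29 | 1.29 | 1.29 | 1.29 | 1.29 |
| Lognormal fit (time ratio 0.51), implied HR | 3.85 | 2.32 | 1.80 | 1.53 | 1.43 |

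The exponential and Gompertz fits share an assumption, not a value (1.38 against 1.29). The mean negative log-likelihood per patient is 3.544 for Gompertz and 3.632 for lognormal (lower is better), so overall fit here favours the proportional model. Lognormal lets the HR vary but never takes it below 1, so it misses the crossing.

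**4. No single HR from lognormal.** Take a lognormal with median 15.24, log-SD π/√6/2.2 = 0.58 and the planned 33% reduction (time ratio 0.67). The implied HR at days 5, 10, 15, 20 and 30 is 3.21, 1.93, 1.61, 1.48 and 1.35.

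**5. Can a frequency be given?** Only under assumptions that the documents do not supply: shapes of 2.2 against 1.3 or 3.5, medians equal or 33% shorter on NR, 20 against 18 patients, a 10%-level test of equal shapes as trigger, and a numeric fit score.

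- With residuals pooled over arms, the trigger fired and a proportional-hazards model was then chosen in 20 to 43% of simulated trials.
- With residuals scored within arm, the range was 4 to 29% on the survival scale and 18 to 55% on the cumulative-hazard scale.
- With truly proportional hazards and pooled residuals it was 5 to 7%.
- SAP 6.1 says of a death before discharge: "In this case, the patient will be censored at the time of death". With an assumed death hazard of 0.0075 per day (9 to 12% censored), the pooled range was 21 to 39%.
- Exponential was chosen in at most 2.5% of pooled-residual runs, so the practical route to the fault is Gompertz.

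SAP 6.5 does not say whether the plots are pooled or by arm. That choice alone moves the range from 20–43% to anywhere within 4–55%.

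**The case against.** The strongest reply is that this is a contingency clause. If the visual check passes, nothing changes. If it fails, the SAP already plans a graph that would show the problem: "A plot of the Kaplan-Meier survivor function (for time to discharge) of each dose and placebo will be presented". It also plans a plot of every individual stay. All of that stands, and it is why the point is minor.

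A second reply is that Cox-Snell plots can react to non-proportionality when drawn by arm. This also stands. The fault in the rule is that it does not require a non-proportional model, not that the plots are blind to one.

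A third is that the effect-measure gap is thin, since a lognormal fit yields a time ratio directly. True, but SAP 6.1 should say so.

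A reader might infer four stronger things that the documents do not support:

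- *That the primary test or decision rule breaks down.* Each candidate gives a P-value for no treatment difference, so SAP 2.4 can still be applied.
- *That choosing the model after unblinding seriously inflates type I error.* The candidates and criterion are pre-specified. Under the assumed numeric trigger and fit rule, null rejection moved from 6.0% (Weibull alone) to 6.9–7.0%.
- *That Weibull should stay primary whatever the check shows.* With the planned effect and proportional hazards it has 76 to 78% power against 60% for lognormal, but the clause is not needed there. With NR medians 33% shorter, shapes 2.2 v 1.3 give Weibull 15 to 16% and lognormal 45%; shapes 2.2 v 3.5 give 99% and 65 to 67%. With equal medians Weibull rejects in 22 to 24% of runs and lognormal in 6 to 7%. Neither model is better throughout.
- *That mortality needs its own rule.* The heading in SAP 6.5 covers Cox models and SAP 6.3 promises only an HR, but nothing here shows that a separate rule is needed.

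**Conclusion.** The concern holds as a narrow drafting fault in SAP 6.5. Exponential and Gompertz, with treatment as the only covariate, keep the constant-hazard-ratio assumption that the clause has just rejected. The selection rule can return one of them, and the only candidate that relaxes the assumption has no named estimate. This rests on the text of SAP 6.1 and 6.5 and on the algebra in step 2. It would not hold for Gompertz if the shape parameter were modelled by treatment, but the SAP does not provide for that.

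Severity is minor. The simulated rates show that the outcome is possible under strong assumed shape differences. They are not the chance of the fault in this trial, which depends on unknown shapes and a judgement by eye.

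**What to change.** - In SAP 6.5, delete exponential and Gompertz as remedies for non-proportional hazards. Keep the lognormal accelerated failure time model, with treatment as the only covariate, as the one pre-specified alternative.
- In SAP 6.1, name the time ratio with 95% confidence interval as the effect measure of that analysis, and time ratio = 1 as its null hypothesis.
- State that the model assumes a constant time ratio, does not cure crossing curves, and is to be read with the planned Kaplan-Meier curves.
- Before unblinding, the sponsor should fix whether the lognormal result replaces the Weibull test, as SAP 6.5 now has it, or is reported beside it. The documents do not settle this.

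The cost is a few sentences in the SAP, with no new data. The downside is that, if the clause is invoked, the lognormal estimate is a time ratio and not the hazard ratio readers were promised.

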2.7 Timing of Outcome Assessments

The target days and visits windows are defined in the protocol as:

Target Day	Definition (Day window)	
-14	Two weeks prior to acute	
	admission to hospital	
Day 1 (Randomization)	Day 1	
Day 3	Target day -1 day/+2 days	
Day 7, 14, 21, 28	Target day± 3 days	
Day 30	Target Day ±10 days	
Day X	Discharge date ± 0 days	
Day X	Withdrawal date ± 0 days	
Day X	Death date ± 0 days	
Day 90	Target day + 90 days/-30days.	
65 weeks	Target day +/-180 days.	
	-14 Day 1 (Randomization) Day 3 Day 7, 14, 21, 28 Day 30 Day X Day X Day X Day X Day 90	

3 Statistical Principles

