6.2 Secondary Continuous Outcomes (Change from Baseline)

Secondary continuous outcomes with change from baseline include grip strength at day 90 and grip strength at day 7. The analyses will be performed on the FAS.

Statistical Method for Steps 1-3

A linear mixed model will be fitted to the three measurements of grip strength (baseline, day 7, and day 90) in each step. The model will contain fixed effects for treatment (NR vs placebo), time point (day 7 vs baseline & day 90 vs baseline), and treatment x time point interaction and a random intercept. Based on the fitted model, we can estimate change from baseline to day 7 and change from baseline to day 90 in each group and the between-group difference in changes from baseline for both time points.

Presentation of Results

We will present the observed mean values and standard deviation for each group at each time point (baseline, day 7, and day 90). We also present the estimated change from baseline to day 7 and the estimated change from baseline to day 90 in each group with 95% confidence intervals, and the estimated between-group differences in changes from baseline to day 7 and to day 90 (the treatment difference), also with 95% confidence intervals.

Missing Data

Missing data on grip strength at either day 7 or day 90 will be handled by the linear mixed model, under the assumption of missing at random. There is no missing data on grip strength at baseline, so all patients will be included in the model.

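### The linear-time fallback for the grip-strength model would tie the day-7 and day-90 effects to one slope and so stop estimating them as separate outcomes

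*SAP*

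**What the plan says.** The outcome table in SAP section 5 gives change in grip strength at 7 days and at 90 days as separate secondary outcomes, and SAP 6.2 repeats this: "Secondary continuous outcomes with change from baseline include grip strength at day 90 and grip strength at day 7". For the analysis, "A linear mixed model will be fitted to the three measurements of grip strength (baseline, day 7, and day 90) in each step". Time enters as two contrasts against baseline, with a treatment-by-time interaction and a random intercept. Besides the change within each arm, the model is meant to supply "the between-group difference in changes from baseline for both time points".

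SAP 6.5 adds two contingencies. Poor fit leads to a log transformation of the outcome. The second is reserved for numerical trouble during fitting, which the SAP considers unlikely. Its remedy reads: "we will remove the two time point variables and substitute it with a single (linear) variable for time". It does not say whether time is then measured in days or by visit number, whether the interaction with treatment is kept, or how the two outcomes would be read from the new model.

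Three other places bear on this. Protocol 10.5.2 makes grip strength the secondary endpoint of special interest. SAP 2.4 lets the 95% confidence interval of a secondary outcome decide whether steps 2 and 3 are carried out. Protocol 6.2.3 takes any NR effect to be in place before the 90-day visit.

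**The concern.** A model with one linear time term has one treatment-by-time coefficient, and two separate differences cannot be recovered from it. Under the fallback the day-7 difference becomes a fixed multiple of the day-90 difference, whatever the data show at day 7. Because baseline, day 7 and day 90 are very unequally spaced, coding time in days makes that multiple small and also lets the day-7 data distort the day-90 estimate.

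At stake are the two estimates for the protocol's secondary endpoint of special interest, and the intervals that gate the lower-dose comparisons for that outcome. An effect that appears early and then levels off is the kind a straight line from baseline to day 90 misstates, and Protocol 6.2.3 makes such a shape plausible.

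**Working it through.** The documents give no SD, effect size or power figure for grip strength, so there is no stated figure to reproduce. The check is algebraic. The effect sizes in kg are assumptions; the ratios and weights do not depend on them.

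**Inputs.** Visits at baseline, day 7 and day 90 (SAP 6.2). Baseline is labelled Day 1 in SAP 2.7, so elapsed time can be coded from 0 or from 1. Let a and b be the true between-group differences in change at day 7 and day 90. Assume that the interaction is kept and the data are complete.

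**Formula.** With a random intercept and the same visit times for everyone, the treatment-by-time coefficient equals the ordinary within-patient least-squares slope. The within-patient correlation drops out.

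slope = Σ(t − t̄)·effect(t) / Σ(t − t̄)²; reported difference at time t = slope × (t − t₀)

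**Days 0/7/90.**
- t̄ = 97/3 = 32.33; deviations −32.33, −25.33, 57.67; sum of squares 1045.4 + 641.8 + 3325.4 = 5012.7.
- slope = (−25.33a + 57.67b)/5012.7.
- Day 90: 90 × slope = −0.455a + 1.035b.
- Day 7: 7 × slope = −0.035a + 0.081b, which is 7/90 = 0.078 of the day-90 value.

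**Days 1/7/90.** The ratio is 6/89 = 0.067. Day 90 is −0.462a + 1.031b, so the picture is nearly the same.

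**Visit number 0/1/2.** The deviations are −1, 0, 1, so slope = b/2. Day 7 is 0.5b and day 90 is exactly b. The ratio is 1/2.

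**Results (kg, day 7 / day 90).**

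| True pattern | True values | Days 0/7/90 | Visit number |
|---|---|---|---|
| Linear in days | 0.23 / 3 | 0.23 / 3.00 | 1.50 / 3.00 |
| Half reached by day 7 | 1.5 / 3 | 0.19 / 2.42 | 1.50 / 3.00 |
| Plateau by day 7 | 3 / 3 | 0.14 / 1.74 | 1.50 / 3.00 |
| Late only | 0 / 3 | 0.24 / 3.11 | 1.50 / 3.00 |
| Early only | 3 / 0 | −0.11 / −1.36 | 0 / 0 |

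For the plateau row: 3 × (−0.4548 + 1.0354) = 1.74, and 1.74 × 7/90 = 0.14.

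**Shared z-value.** Each reported difference and its standard error are the slope and its standard error times the same constant. Both intervals therefore include or exclude zero together, under every coding.

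**Precision.** With residual variance s² and groups of 18 and 20 (step 1), the planned model's day-7 SE is s√[2(1/18 + 1/20)]. The day-coded fallback gives 7s√[(1/18 + 1/20)/5012.7]. The ratio is 7/√(2 × 5012.7) = 0.07. With an assumed s = 4 these are 1.84 and 0.13. The fallback interval at day 7 is thus far narrower, around a value that is biased unless the effect is linear.

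**Simulation check** (assumed between-patient SD 9 and residual SD 4, 18 against 20 patients, 100 runs per scenario, Monte Carlo error about 0.2). For a true effect of 4 at both visits and no missing data, categorical time gave means of 3.7 and 3.7, and linear days gave 0.17 and 2.19; the formula gives 0.18 and 2.32. With 20% of day-90 values missing, linear days gave 0.19 and 2.49. The planned categorical model fitted in all 600 simulated data sets.

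**The case against.** The strongest reply is that this rule will probably never be used. It is triggered only by numerical failure, which the SAP calls unlikely for so simple a model, and the simulation agrees. The outcome is secondary, estimated without hypothesis tests and regarded as supportive, and the primary analysis is untouched. All of that stands and keeps the point small.

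It also stands that the size of the problem depends on choices the SAP leaves open. A reader might infer that the SAP fixes the day-7 effect at 7/90 of the day-90 effect. It does not: that ratio follows from coding time as days from baseline, and other codings give 6/89 or 1/2. A reader might also infer that both estimates would always be wrong. The documents do not support that. There is no bias if the effect is linear on the scale used. With visit-number coding and complete data, day 90 is estimated exactly and only day 7 is constrained. In days, a late-only effect moves day 90 by just 0.11 kg on 3.

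Nor would an early effect be hidden. SAP 6.2 presents observed means and SDs by group at each visit, and SAP 6.5 compares observed with predicted values. However, the only remedy SAP 6.5 gives for misfit is a log transformation, which would not restore separate visit effects.

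The open scale does not rescue the rule, since no common coding gives two separate estimates. If the interaction were dropped with the time contrasts, no between-group difference in change would be estimated at all.

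**Conclusion.** The fallback is a defective rule. If it is used with the interaction kept, the day-7 and day-90 differences are one quantity reported at two scales, with a common z-value. The day-7 estimate is biased unless the effect is linear on the chosen scale. With time in days, day 90 is biased as well under a non-linear effect, from slightly (3.11 for a true 3) to severely (1.74 for a true 3, or −1.36 for a true 0 after an early 3 kg effect).

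These figures assume complete data, nominal visit days and assumed effect sizes. Using actual visit days within the wide windows of SAP 2.7 would change the weights, but there would still be only one slope. The protocol's expectation that effects are in place before day 90 makes a straight line doubtful, though it does not rule one out.

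Importance is low: an unlikely contingency for a supportive outcome. It is still worth correcting, because the outcome is the one of special interest and its interval decides whether the lower doses are examined for it.

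**What to change.** Delete the linear-time substitution from SAP 6.5. State instead that time stays categorical with the treatment-by-time interaction, and that numerical problems are handled in this order:

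1. Change the optimiser or the covariance structure, for example a marginal model with compound-symmetry or unstructured residuals. This keeps both outcomes and the missing-at-random handling planned in SAP 6.2.
2. Only if that fails, fit a baseline-adjusted linear regression at day 7 and another at day 90. These need no iterative fit and keep both outcomes.

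The cost is a sentence or two in the SAP. The drawback lies in the last resort: patients who miss a visit drop out of that visit's regression.
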